8.7.2.4.3 Analysis of Exploratory Endpoint

Not applicable.

8.7.2.5 Sensitivity Analysis

8.7.2.5.1 Subgroup Analysis

Subgroups of interest such as males and females, specific age groups, renal and hepatic impairment, and concomitant medications, may be undertaken if enough subjects are available. If the number of subjects is insufficient, it will be replaced by listing table.

8.7.3 Analysis of Safety Endpoint(s)/Outcomes(s)

The safety analysis set will contain all subjects who have received at least 1 dose of sotorasib in accordance with the approved therapeutic indications, dosage, and administration in South Korea and completed at least 1 safety follow-up. Analysis of safety endpoints will be conducted as described in Section 8.7.2.4.1.

The 6-month cumulative incidence of adverse events will be summarized to include all recorded treatment-emergent adverse events from the first dose of sotorasib or any worsening of medical conditions initially experienced before the first dose of sotorasib. This summary for adverse events will be performed for the following categories:

- all adverse events and adverse drug reactions
- serious adverse events and serious adverse drug reactions
- unexpected adverse events and unexpected adverse drug reactions
- unexpected serious adverse events and unexpected serious adverse drug reactions
- adverse events leading to sotorasib discontinuation
- fatal events

8.8 Quality Control

The Amgen representative(s) and regulatory authority inspectors are responsible for inspecting the various records of the study (eg, eCRFs and other pertinent data) provided that subject confidentiality is respected.

Amgen or its designee is responsible for verifying the eCRFs to confirm adherence to the protocol, completeness, accuracy, and consistency of the data and adherence to local regulations on the conduct of surveillance studies.

The investigator agrees to cooperate with Amgen or contract research organization staff to ensure that any problems detected in the course of the study, including delays in completing eCRFs, are resolved. In accordance with the sponsor's audit plans, this study may be selected for audit by representatives from Amgen's Quality, Compliance, and Audit function (or designees).

8.9 Limitations of the Research Methods

The current study plans to adopt rigorous observational data collection methods for the study.

8.9.1 Internal Validity of Study Design

Information bias and missing or incomplete data is a potential risk for information bias and efforts will be made to collect complete data through the use of clear instructions to investigators regarding the completion of eCRFs.

There is no systematic review or systematic method of adverse event collection. Adverse events are collected as part of a regular interaction with the subject as would be in normal practice. Therefore, adverse events collected are subject to reporting bias, but such effect is inherent to real-world surveillance.

8.9.1.1 Measurement Error(s)/Misclassification

As with any surveillance study that relies on data entry from multiple sites, there is the potential for misclassifying adverse events and adverse drug reactions. Misclassifications can impact the validity of outcomes as well as affect overall conclusions.

8.9.1.2 Information Bias

Missing or incomplete data is a potential risk for information bias and efforts will be made to collect complete data through the use of clear instructions to investigators regarding the completion of eCRFs.

There is no systematic review or systematic method of adverse event collection. Adverse events are collected as part of a regular interaction with the subject as would be in normal practice. Therefore, adverse events collected are subject to reporting bias, but such effect is inherent to real-world surveillance.

8.9.1.3 Selection Bias

This study is an observational study in a real-world setting. The inclusion criteria are intended to enroll all patients prescribed sotorasib in clinical practice according to the approved therapeutic indications, dosage, and administration in South Korea. Consecutive enrollment will be performed to potentially reduce selection bias.

8.9.1.4 Confounding

Not applicable.

8.9.2 External Validity of Study Design

The participating medical centers are expected to represent approximately over 80% of the total patients treated with sotorasib in South Korea, so it is expected that the results from current study are generally extendable to the general population of patients treated with sotorasib in South Korea. Also, as with other studies, this study only includes patients who provide consent to participate, and patients that did not participate in this study may be different compared to those who did.

8.9.3 Limitations Due to Missing Data and/or Incomplete Data

Some subjects may discontinue the study, creating missing or incomplete data for the study endpoint assessments. Such discontinuations may be related or informative to the outcomes. Consequently, there is a risk for bias due to missing completed data and lack of robust data to analyze results.

8.10 Other Aspects

All written information and other material to be used by subjects and investigative staff must use vocabulary and language that are clearly understood.

9. Protection of Human Subjects

9.1 Informed Consent

An initial sample informed consent form (ICF) is provided for the investigator or designee to prepare the informed consent document to be used at his or her site. Updates to the sample ICF are to be communicated formally in writing from the Clinical Study Manager to the investigator or designee. The written ICF is to be prepared in the language(s) of the potential patient population.

Before a subject's participation in the study, the investigator or designee will explain to the subject, or his/her legally authorized representative, the aims, methods, anticipated benefits, and potential hazards of the study, and answer all questions regarding the study.

The acquisition of informed consent is to be documented in the subject's medical records, and the ICF is to be signed and personally dated by the subject or a legally authorized representative and by the person who conducted the informed consent discussion. The original signed ICF is to be retained in accordance with institutional

policy, and a copy of the ICFs must be provided to the subject or the subject's legally authorized representative.

If local regulations do not require an informed consent to be signed but mandate that the subject is notified about the study, the investigator or designee should document the notification process in the subject's medical record.

9.2 Institutional Review Board/Independent Ethics Committee

A copy of the protocol, proposed ICF, other written patient information, and any proposed advertising material must be submitted to the Institutional Review Board (IRB)/Independent Ethics Committee (IEC) for written approval. A copy of the written approval of the protocol and ICF must be received by Amgen before the study can be executed. The investigator must submit and, where necessary, obtain approval from the IRB/IEC for all subsequent protocol amendments and changes to the informed consent document. The investigator is to notify the IRB/IEC of deviations from the protocol or serious adverse event(s) occurring at the site and other adverse event reports received from Amgen, in accordance with local procedures. The investigator is responsible for obtaining annual IRB approval and IRB/IEC renewal throughout the duration of the study. Copies of the investigator's reports, where applicable by local regulations and the IRB/IEC continuance of approval must be sent to Amgen.

Any protocol amendments will be submitted to the local IRB for their review and approval. Annual IRB approval/renewal throughout the duration of the study will be obtained and copies of the IRB continuance of approval will be sent to Amgen.

9.3 Patient Confidentiality

The investigator must ensure that the subject's confidentiality is maintained for documents submitted to Amgen.

Subject will be assigned a unique identifier by the sponsor or delegate. Any subject records or datasets that are transferred to the sponsor will contain the identifier only; subject names or any information which would make the subject identifiable will not be transferred.

For serious adverse events reported to Amgen, subjects are to be identified by their unique subject identification number, initials (for faxed reports, in accordance with local laws and regulations), and age (in accordance with local laws and regulations).

Documents that are not submitted to Amgen (eg, signed ICFs) are to be kept in confidence by the investigator, except as described below.

In compliance with local country regulations, it is required that the investigator and institution permit authorized representatives of the company, of the regulatory agency(s), and the IRB/IEC direct access to review the subject's original medical records for verification of data. Direct access includes examining, analysing, verifying, and reproducing any records and reports that are important to the evaluation of the study. The investigator is obligated to inform and obtain the consent of the subject to permit such individuals to have access to his/her study-related records, including personal information.

9.4 Subjects Decision to Withdraw

Subjects have the right to withdraw from the study at any time and for any reason without prejudice to their future medical care by the physician or at the institution.

Withdrawal of consent for a study means that the subject does not wish to or is unable to continue further study participation. Subject data up to withdrawal of consent will be included in the analysis of the study and, where permitted, publicly available data can be included after withdrawal of consent. The investigator is to discuss with the subject appropriate steps for withdrawal of their consent from the study.

10. Collection, Recording, and Reporting of Safety Information and Product Complaints

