8.1 Study Design

This is an observational multicenter prospective cohort study in subjects who are prescribed sotorasib within the approved indication in a post-marketing setting in South Korea.

Subjects that meet the eligibility criteria (Section 8.2.3) and sign the informed consent will be enrolled. Subjects will be seen by their physician per local standard of care and should receive sotorasib in accordance with the approved therapeutic indication, dosage, and administration in South Korea. Adverse events, serious adverse events, adverse drug reactions, serious adverse drug reactions, adverse events leading to discontinuation of sotorasib, fatal events, other safety findings and spontaneously reported product complaints will be collected for each subject from their first dose of sotorasib on day 1 through the end of study (EOS). Treatment responses will be

collected after day 1 through EOS. Six-month cumulative subject incidence of adverse events will be reported and summarized. Unexpected adverse events, unexpected serious adverse events, unexpected adverse drug reactions, and unexpected serious adverse drug reactions will be analyzed from the collected adverse events/serious adverse events/adverse drug reactions/serious adverse drug reactions as part of a special analysis. Overall response rate is defined as the proportion of patients with a Best Overall Response (BOR) of confirmed complete response (CR) or confirmed partial response (PR) and will also be reported and summarized. The investigators should evaluate the clinical outcome of each subject during the surveillance period and assign one of the following descriptions: improved, not changed, disease progression, or unable to evaluate. End of study is defined as completing 6 months of sotorasib use, discontinuation of sotorasib plus 30 days, withdrawal of consent, death, or lost to follow-up, whichever occurs first. All data collected for the purpose of this study will be entered into the eCRF.

For a full list of data elements, including the timing for each data abstraction, please refer to the schedule of data collection in Table 1.

Table 1. Schedule of Data Collection

			Visit(s) Following Day 1
	Baseline Eligibility Periodª	Start of Sotorasib Day 1ª	Data will be collected from medical records at each subsequent site visit (expected to occur at ~ day 21, month 2, month 4, and month 6) through EOS
GENERAL ASSESSMENTS			
Eligibility Review	Х	Х	

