8.4 Data Sources

The data source for this study is subject medical records. These medical records may include a combination of paper and electronic sources. Study site staff will extract data from the medical records into the study-specific electronic database provided by the sponsor.

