10.2 Safety Collection, Recording and Submission to Amgen Requirements

This study is collecting information from healthcare professionals and patient's medical records prospectively.

All reportable events (adverse events, product complaints, and other safety findings) considered to have occurred following subject exposure to sotorasib will be collected from the time of first dose to 30 days after final dose of sotorasib or EOS, whichever occurs first. The investigator is responsible for ensuring that all reportable events they become aware of during the prospective period, are recorded in the subject's study documentation. It is the investigator's responsibility to evaluate whether an adverse event is related to an Amgen product prior to reporting the adverse event to Amgen. If further safety related data is needed to fulfill any regulatory reporting requirements for a reportable event, then additional information may need to be collected from the subject's records after the subject ends the study. All reportable events must be submitted as individual safety reports to Amgen Safety or delegate via the applicable Safety Reporting Form (paper or electronic form) within the timelines stated in Table 2 below.

Reportable Events/Event Type	Reporting Timeframe
 Serious Adverse Events (related and non-related) Product Complaints (serious and non-serious) Other Safety Findings (serious and non-serious) Pregnancy and/or Lactation Exposure 	 Within 1 business day from when Investigator first becomes aware of the event
 Non-serious Adverse Events (related and non-related) 	 Within 15 calendar days from when Investigator first becomes aware of the event

 Table 2. Types of Safety Data to be Collected and Reported in Primary Data

 Collection Studies Collecting All Reportable Events

Reportable events that are suspected to be related to any Amgen medicinal product, combination product, or device where there is no exposure to state studied/supplied Amgen product(s) should be spontaneously reported to Amgen within 1 business day of investigator/vendor awareness. A list of all Amgen medicinal products can be found in the following link: https://wwwext.amgen.com/amgen-worldwide.

To spontaneously report a reportable event to Amgen, refer to the following link to locate your Local Amgen contact information by country: https://wwwext.amgen.com/contact-us/product-inquiries.

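### Section 9.4 counts inability to continue as withdrawal of consent, which closes safety collection at once and may under-count late adverse events and deaths

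*Protocol*

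**What the plan says.** Protocol Section 9.4 (Subjects Decision to Withdraw) gives the definition: "Withdrawal of consent for a study means that the subject does not wish to or is unable to continue further study participation". It keeps data up to withdrawal and adds that "where permitted, publicly available data can be included after withdrawal of consent".

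Section 8.1 defines end of study as six months of sotorasib use or the earliest of several other triggers: "discontinuation of sotorasib plus 30 days, withdrawal of consent, death, or lost to follow-up, whichever occurs first". Sections 8.2.1, 8.2.6, 8.3.2 and 8.7.1.2 repeat this follow-up rule. Stopping sotorasib carries 30 further days of follow-up; withdrawal of consent carries none.

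Section 10.2 sets the safety window. Reportable events "will be collected from the time of first dose to 30 days after final dose of sotorasib or EOS, whichever occurs first". It also allows that, for regulatory reporting of a reportable event, "additional information may need to be collected from the subject's records after the subject ends the study".

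On the source, Section 8.4 says: "The data source for this study is subject medical records". Section 8.7.2.2 says that missing safety data are generally not imputed. Section 8.9.3 says of subjects who leave the study: "Such discontinuations may be related or informative to the outcomes".

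**The concern.** A decision to revoke consent and an inability to continue are different things. Only the first obliges the sponsor to stop abstracting records. Section 9.4 merges them and so gives the second the consequence of the first: immediate end of study and closure of safety collection.

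The study needs no such rule. Visits follow routine practice, no exact follow-up dates are fixed (Section 8.7.1.2), and the data are taken from charts. A subject who cannot take part further, but whose consent stands, can still have the chart abstracted as far as it remains available. Sections 8.2.3.1 and 9.1 also provide for an authorized representative, so consent need not lapse because the subject cannot act.

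The primary safety outcomes are at stake, since fatal and serious events are among them (Section 8.3.2). If follow-up is cut short for reasons related to outcome, the reported incidence is too low. Two sites could also classify the same subject differently and so count different events. Section 8.9.3 accepts that discontinuation may be informative; this definition adds a source of it that can be avoided.

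**Working it through.** The protocol states no withdrawal rate, expected death rate or precision target on this point, so there is no figure of its own to reproduce. The check is a trace through the rules, followed by arithmetic for scale.

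**Step 1: the rule chain.**

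| Reason recorded | End of study (8.1) | Safety collection closes (10.2) |
|---|---|---|
| Stopped sotorasib, consent stands | last dose + 30 days | last dose + 30 days |
| Unable to continue (withdrawal under 9.4) | date of that record | date of that record |

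The first trigger to occur applies, so the second row overrides the first whenever both fit.

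**Step 2: an illustrative subject (days chosen for illustration).** Last dose on day 60, recorded as unable to continue on day 63, death in the chart on day 75.
- Recorded only as stopping sotorasib: window closes on day 60 + 30 = 90. Since 75 < 90, the death counts.
- Recorded as unable to continue: window closes on day 63. Since 75 > 63, the death falls outside scheduled collection. Follow-up lost is 90 − 63 = 27 days.

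A subject still taking sotorasib when so recorded could lose more, up to the rest of the six months.

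**Step 3: effect on the estimate.** The Safety Analysis Set needs one dose and one safety follow-up (8.7.1.2), so a subject with both stays in the denominator. Six-month incidence is a frequency and percentage (Abstract, Data Analysis). With no imputation, an uncollected death counts as no event. The error from this source can only lower the incidence.

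**Step 4: scale at the minimum sample.** Section 8.5 sets a minimum of 25 subjects and Section 8.7.2.1 specifies exact 95% intervals. One subject is 1/25 = 4.0 percentage points. Clopper-Pearson intervals:

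| Fatal events | Incidence | Exact 95% CI |
|---|---|---|
| 5/25 | 20.0% | 6.8 to 40.7 |
| 4/25 | 16.0% | 4.5 to 36.1 |
| 2/25 | 8.0% | 1.0 to 26.0 |
| 1/25 | 4.0% | 0.1 to 20.4 |

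**Step 5: proportional effect.** Observed incidence = true incidence × (1 − share of deaths lost). Both inputs are assumptions.

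| True incidence | 10% of deaths lost | 25% lost | 50% lost |
|---|---|---|---|
| 10% | 9.0% | 7.5% | 5.0% |
| 20% | 18.0% | 15.0% | 10.0% |
| 30% | 27.0% | 22.5% | 15.0% |

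The protocol does not indicate which column applies.

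**The case against.** The strongest reply is contextual. Section 9.4 is headed as the subject's decision, opens with the right to withdraw and ends with the investigator discussing the steps with the subject. In that setting withdrawal is an act of the subject, and no section tells a site to declare an ill subject withdrawn. Because participation asks little beyond routine care, few subjects may be unable to continue at all. A declining subject who stops sotorasib fits the trigger with the 30-day extension.

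Much of this stands. A reader might infer that the sickest subjects systematically lose the window and that their deaths drop out of the fatal-event endpoint. The protocol does not support that: it never says that illness makes a subject unable to continue. Deaths and serious events before the recorded withdrawal are counted. Because the endpoint is subject incidence, a subject with an earlier serious event already counts for that outcome.

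Two provisions also allow some recovery. Section 9.4 admits public data after withdrawal, but this is optional, applies only where permitted, does not cover private charts, and is not said to feed the fatal-event endpoint. Section 10.2 allows later record collection, but to complete regulatory reporting of a reportable event, not to keep looking for new ones.

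The contextual reading does not remove the defect. The sentence as written covers inability, and the end-of-study rule applies the earlier trigger. A site that follows the text may close follow-up on a subject who never revoked consent.

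**Conclusion.** The point holds as a wording defect with a real consequence for follow-up. Sections 9.4, 8.1 and 10.2 together allow a subject who has not revoked consent to leave safety collection at once. Late adverse events and deaths may be under-counted, and capture depends on the reason recorded.

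The size cannot be derived from the protocol. A reader might multiply plausible rates: 40 to 60% stopping sotorasib within six months, 10 to 20% of those recorded as unable, and 30 to 50% of those with a fatal or serious event within 30 days of the last dose. That gives 0.4 × 0.1 × 0.3 = 1.2% to 0.6 × 0.2 × 0.5 = 6.0%. This range should not be used. All three inputs are assumed, fatal and serious events are pooled, and events before the recorded withdrawal are treated as lost. What can be said is that each missed death is 4 percentage points at n = 25 and proportionately less in a larger study. That is small beside the width of the exact interval, but the interval does not allow for a one-directional error of this kind.

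The conclusion assumes that at least some sites would use the inability clause as written. The change is worth making because it corrects a stated follow-up rule at little cost.

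**What to change.** In Section 9.4, delete the words *or is unable to*, and state that withdrawal of consent means only an expressed decision by the subject or the authorized representative.

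Add one sentence: inability to continue does not by itself end record abstraction, which goes on within the existing follow-up window as far as records remain available and loss to follow-up has not occurred. Record inability as a reason separate from withdrawal of consent.

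The 30-day and six-month limits, the loss-to-follow-up trigger and treatment all stay as they are. The cost is a short amendment, one reason category in data capture and slightly more chart abstraction for a few subjects under consent already given. The change will not recover outcomes of subjects whose care moves to a place whose records the site cannot see.

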10.1 Definition of Reportable Events

10.1.1 Adverse Events

An adverse event is any untoward medical occurrence in a subject/patient administered a pharmaceutical product(s) irrespective of a causal relationship with this treatment.

An adverse event can therefore be any unfavorable and unintended sign (including an abnormal laboratory finding, for example), symptom, or disease temporally associated with the use of a product(s), whether or not considered related to the product(s). The definition of an adverse event includes:

- Worsening of a pre-existing condition or underlying disease
- Events associated with the discontinuation of the use of a product(s), (eg, appearance of new symptoms)

It is the investigator's responsibility to evaluate whether an adverse event is related to an Amgen product prior to reporting the adverse event to Amgen.

An adverse drug reaction is a noxious and unintended response to a pharmaceutical product(s) administration normally. Adverse drug reactions are adverse events

considered related to sotorasib by the investigator, including those with unknown relationship.

Unexpected adverse events or unexpected adverse drug reactions means adverse events or adverse drug reactions not reflected in precautions of approved local label.

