8.3.2 Outcome Assessment

- Primary outcome measure: Incidence of adverse events, serious adverse events, adverse drug reactions, serious adverse drug reactions, unexpected adverse events, unexpected serious adverse events, unexpected adverse drug reactions, unexpected serious adverse drug reactions, adverse events leading to sotorasib discontinuation, and fatal events throughout the treatment/observation period along with their severity, action taken, and causal relationship with sotorasib will be assessed for any subject who has received at least 1 dose of sotorasib according to the approved therapeutic indications, dosage and administration in South Korea and completed at least 1 safety follow-up. Six-month cumulative subject incidence of the adverse events will be reported and summarized. All adverse events will be graded using the most recent CTCAE version.
- Secondary outcome measure: ORR is defined as the proportion of patients with a BOR of confirmed CR or confirmed PR. To assess ORR, a real-world RECIST based response assessment will be utilized since this is standard for clinic practice in South Korea. Subjects will be categorized according to their BOR during the follow-up period using RECIST criteria v1.1 or a more recent version as noted in the subject's medical records. Subjects will be assigned to one of the following best response categories during each assessment:
 - CR or PR
 - SD
 - PD
 - not evaluable disease (NE)

Each response start date (start date of confirmed PR or better response) or date of disease progression will be assessed at month 2, month 4, and month 6 (EOS visit). Subjects will be followed from their first dose of sotorasib through the completion of 6 months of sotorasib use, discontinuation of sotorasib plus 30 days, withdrawal of consent, death, or lost to follow-up, whichever occurs first.

In addition, investigators should evaluate the clinical outcome of each subject during the surveillance period and assign one of the following descriptions:

- improved
- not changed
- disease progression
- unable to evaluate

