10.1.2 Serious Adverse Events

A serious adverse event/serious adverse device effect is any adverse event/adverse device effect as defined above that meets at least one of the following serious criteria:

- is fatal
- is life threatening (places the subject at immediate risk of death)
- requires in-patient hospitalization or prolongation of existing hospitalization
- results in persistent or significant disability/incapacity
- is a congenital anomaly/birth defect
- is an "other medically important serious event" that does not meet any of the above criteria

A hospitalization meeting the regulatory definition for "serious" is any in-patient hospital admission that includes a minimum of an overnight stay in a healthcare facility.

"Other medically important serious events" refer to important medical events that may not be immediately life threatening or result in death or hospitalization but may jeopardize the subject or may require intervention to prevent one of the other outcomes listed in the definition above. Examples of such events could include allergic bronchospasm, convulsions, and blood dyscrasias, drug-induced liver injury, events that necessitate an emergency room visit, outpatient surgery, or other events that require other urgent intervention.

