10.1.3 Other Safety Findings

Other safety findings (regardless of association with an adverse event) include:

- medication errors, overdose/underdose, whether accidental or intentional, misuse, addiction, or abuse involving an Amgen product
- use of an Amgen product while pregnant and/or breast feeding
- transmission of infectious agents
- reports of uses outside the terms for authorized use of the product including off-label use
- accidental or occupational exposure
- any lack or loss of intended effect of the product(s)

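### Lung cancer progression falls within the adverse-event definition, so the serious, unexpected, discontinuation and fatal incidences mix disease course with drug safety

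*Protocol*

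**What the plan says.** Protocol Section 10.1.1 includes "Worsening of a pre-existing condition or underlying disease" in the definition of an adverse event. Section 8.7.3 takes into the 6-month cumulative incidence both treatment-emergent events and "any worsening of medical conditions initially experienced before the first dose of sotorasib". The Data Analysis part of the abstract (Section 4) has a similar rule.

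Other definitions decide which further endpoints an event enters:

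- **Unexpected** (Section 10.1.1): "adverse events or adverse drug reactions not reflected in precautions of approved local label". The label itself is not reproduced.
- **Serious** (Section 10.1.2): the event "meets at least one of the following serious criteria", among them death, hospitalisation and medical importance.
- **Adverse drug reaction** (Section 10.1.1): events "considered related to sotorasib by the investigator, including those with unknown relationship".
- **Fatal events** (Sections 8.3.2 and 8.7.3): a primary outcome with no restriction on cause.

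Progression is also collected as effectiveness. Section 8.3.2 dates it at months 2, 4 and 6 and makes it a category of the investigator's clinical outcome, and Section 8.7.2.4.2 counts it as PD. Section 10.1.3 separately lists failure or loss of the product's effect among the other safety findings.

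**The concern.** Subjects enter the study because they are prescribed sotorasib for its approved cancer indication. Growth of that cancer is, on a plain reading, a worsening of the underlying disease. Nothing in the protocol excludes it from the adverse-event totals or totals it separately, and nothing says how an adverse event is to be told apart from PD or from lack of effect.

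Six of the ten primary endpoints have no relatedness filter: AE, SAE, unexpected AE, unexpected SAE, AE leading to discontinuation, and fatal events. A headline rate for these would reflect partly how often NSCLC progresses within the follow-up window and partly what the drug does.

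Uneven recording adds to this. Section 8.9.1 concedes that adverse events are not collected systematically, and Section 8.9.1.1 concedes possible misclassification. With about 20 sites and possibly only 25 subjects, differing site habits could shift the headline incidences. Table 2 in Section 10.2 also sets different reporting times for other safety findings (1 business day) and non-serious adverse events (15 calendar days), and a non-serious progression could be filed as either.

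**Working it through.** **1. The plan's own figure.** There is none to reproduce. No stated incidence or precision depends on this definition, and the minimum of 25 subjects rests on regulation.

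**2. One progression followed through the definitions.**

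- AE: yes (Sections 10.1.1 and 8.7.3).
- Unexpected AE: yes, if the label's precautions do not list it.
- SAE: only if a Section 10.1.2 criterion is met; progression seen only on a scan need not meet one.
- Unexpected SAE: only if both of the previous conditions hold.
- AE leading to discontinuation: if sotorasib is stopped for it.
- Fatal event: if it causes death.
- The four ADR endpoints: only if judged related or of unknown relationship.

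**3. Size.** Let g be the incidence without progression, p the probability of progression in the window, and s the share of progressions that meet the endpoint. Assuming independence, the reported incidence is T = 1 − (1 − g)(1 − p·s). The share of counted subjects who are there only because of progression is (T − g)/T.

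Inputs:

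- p: 30% to 62.9%, assumed. The upper value is 100 − 37.1, the complement of the pivotal-study response rate in Section 6.1. It is an illustration and not a bound, because non-responders include stable disease and responders can progress later.
- s: 20% to 80%, assumed; 100% for any AE.
- g for discontinuation: 7.1%, the treatment-related figure for the pivotal study in Section 6.1, used as a stand-in.
- All other g: assumed.

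Worked ends of the range for discontinuation:

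- Low: 1 − 0.929 × (1 − 0.30 × 0.20) = 1 − 0.929 × 0.940 = 12.7%
- High: 1 − 0.929 × (1 − 0.629 × 0.80) = 1 − 0.929 × 0.4968 = 53.8%

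| Endpoint | g | T, low to high | Share due only to progression |
|---|---|---|---|
| AE leading to discontinuation | 7.1% | 12.7% to 53.8% | 44% to 87% |
| Unexpected SAE | 5% | 10.7% to 52.8% | 53% to 91% |
| Unexpected SAE | 10% | 15.4% to 55.3% | 35% to 82% |
| SAE | 20% | 24.8% to 60.3% | 19% to 67% |
| SAE | 30% | 34.2% to 65.2% | 12% to 54% |
| Any AE (s = 100%) | 80% | 86.0% to 92.6% | 7% to 14% |
| Any AE (s = 100%) | 95% | 96.5% to 98.1% | 2% to 3% |

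In 25 subjects, the discontinuation row means 1.8 expected subjects without progression and 3.2 to 13.5 with it.

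**4. Unexpected AE.** No seriousness condition applies here. Suppose 10 of 25 subjects progress, each progression is recorded as an AE, the label omits progression, and one other subject has a different unexpected event. The total is 11/25 = 44%; without progression it is 1/25 = 4%. All these inputs are invented for illustration.

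**5. Precision.** The exact 95% interval is 1.0-26.0% for 2/25 and 21.1-61.3% for 10/25. These intervals express sampling error only. They do not show how much of a rate is progression, or how unevenly sites recorded it.

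**The case against.** The strongest reply is that this is table design, which belongs in a statistical analysis plan not shown here. That plan could indeed add a with-and-without split. But Section 10.1.1 is a stated rule that determines what sites record, and a later analysis cannot repair uneven recording.

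A second reply is that a reader can already see progression. This is largely true. Section 8.7.2.1 tabulates events by SOC and PT, Section 8.7.2.4.1 provides listings, and the safety form in Appendix C has a cause-of-death field. A new kind of event keeps its own PT row and count. So a reader who inferred that a genuine signal would be hidden, or that progression cannot be separated at all, would go too far. What remains mixed is the overall incidence for each endpoint and its interval.

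Third, overlap is partly intended. Section 10.1.3 lists other safety findings whether or not an adverse event is associated, the adverse-event definition is independent of cause, and an all-cause fatal count is what that endpoint states. Overlap alone is therefore no error; the weakness is the missing boundary and the missing split.

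Finally, a reader might infer that progression swamps all the primary safety endpoints. The documents do not support that. Four of the ten need a related or unknown relationship, and they include unexpected ADR and unexpected serious ADR, which are aimed most directly at new drug risks. Any-AE incidence is probably near its ceiling already.

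**Conclusion.** The point holds in limited form and should be corrected. As written, progression of the treated NSCLC enters the six primary endpoints that have no relatedness filter. It matters most for discontinuation, unexpected AE, unexpected SAE and fatal events, moderately to strongly for SAE, and little for any AE.

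Over the assumed ranges, discontinuation moves from 7.1% to about 13-54%, and unexpected SAE from an assumed 5% to about 11-53%. These figures rest on assumed progression rates and shares, independence, progression being recorded as defined and, for the unexpected endpoints, a label that does not list it. The protocol gives no progression rate and no PFS, so they show how large the effect could be and do not predict it. For the same reason, a claim that unexpected-AE incidence could not fall below some 30-60% would only restate an assumption. Nor is progression automatically serious or unexpected: the first needs a Section 10.1.2 criterion, and the second depends on a label that cannot be checked here.

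**What to change.** Keep collection and expedited reporting unchanged, and make two changes.

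1. In Section 10.1.1, state one rule for how sites record progression of the treated NSCLC and death from it, relative to PD (Sections 8.3.2 and 8.7.2.4.2) and to lack of effect (Section 10.1.3).
2. In Sections 8.7.2.4.1 and 8.7.3, report the incidences of AE, SAE, unexpected AE, unexpected SAE, AE leading to discontinuation and fatal events twice: for all events, and excluding a list of MedDRA progression terms fixed before the first periodic report. Split fatal events into disease progression and other causes.

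The second change alone would not be enough, because an extra row does not cure uneven recording. The cost is one term list, one extra row per table, and a cause-of-death check that uses the field already on the safety form.
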